7.6.2. Fractures

In the Phase 2 study (B152006), following 12 weeks of dosing with ertugliflozin, there was a suggestion of an increase in markers of bone resorption, though there did not appear to be a clear dose-dependent effect with increasing dose of ertugliflozin. In totality, the clinical relevance of these findings remains unclear. However, the effect of ertugliflozin on bone mineral density will be evaluated in a Phase 3 trial. In addition, in this trial and throughout the Phase 3 program, all clinical fractures will be adjudicated by an external independent panel of physicians (radiologists) experienced in assessing fractures. The radiologists will review the radiograph(s) (if available) and, where applicable the local radiologist report and other source documents and confirm the presence of the fracture, location of fracture, number of fractures, and type of fracture (ie, high-trauma, low-trauma, pathological fracture, stress fracture, and other fracture). The panel will be blinded to treatment assignment. A Fracture Adjudication Charter will describe the precise mandates and procedures to be used for the adjudication of clinical fractures.

7.6.3. Pancreatitis

Type 2 diabetes is a risk factor for pancreatitis. As part of the overall assessment of the safety profile of ertugliflozin, events of pancreatitis reported in this trial and throughout the Phase 3 program will be adjudicated by an independent external panel of physicians experienced in assessing pancreatic disease. The panel will be blinded to treatment assignment. A Pancreatitis Adjudication Charter will describe the precise mandates and procedures to be used for the adjudication of pancreatitis.

7.6.4. Liver Injury

As hepatic safety is a significant issue in drug development, all events that meet pre-specified criteria for potentially important hepatotoxicity will be adjudicated by an external independent panel of physicians experienced in assessing liver injury. The panel will be blinded to treatment assignment and will assess causality. A Liver Injury Adjudication Charter will describe the precise mandates and procedures to be used for assessing liver injury and assigning causality.

7.6.5. Renal Failure

Ertugliflozin, an SGLT2 inhibitor, increases urinary glucose excretion leading to an osmotic diuresis, and has the potential to reduce estimated glomerular filtration rate (eGFR), due to the effect on plasma volume (ie, a hemodynamic effect on eGFR). As part of the overall assessment of renal safety, events reported in this trial and throughout the Phase 3 program

that meet pre-specified criteria for potentially important renal failure events will be adjudicated by an external independent panel of physicians experienced in adjudication of renal events. The panel will be blinded to treatment assignment and will assess causality. A Renal Failure Adjudication Charter will describe the precise mandates and procedures to be used for assessing renal failure and assigning causality.

8. ADVERSE EVENT REPORTING

8.1. Assessing and Recording Adverse Events

An adverse event is defined as any untoward medical occurrence in a patient or clinical investigation subject administered a pharmaceutical product and which does not necessarily have to have a causal relationship with this treatment. An adverse event can therefore be any unfavorable and unintended sign (including an abnormal laboratory finding, for example), symptom, or disease temporally associated with the use of a medicinal product or protocol-specified procedure, whether or not considered related to the medicinal product or protocol-specified procedure. Any worsening (ie, any clinically significant adverse change in frequency and/or intensity) of a preexisting condition that is temporally associated with the use of the Sponsor's product, is also an adverse event.

Changes resulting from normal growth and development that do not vary significantly in frequency or severity from expected levels are not to be considered adverse events.

Examples of this may include, but are not limited to, teething, typical crying in infants and children and onset of menses or menopause occurring at a physiologically appropriate time.

Sponsor's product includes any pharmaceutical product, biological product, device, diagnostic agent or protocol-specified procedure, whether investigational (including placebo or active comparator medication) or marketed, manufactured by, licensed by, provided by or distributed by the Sponsor for human use.

Adverse events may occur during the course of the use of the Sponsor's product in clinical trials or within the follow-up period specified by the protocol, or prescribed in clinical practice, from overdose (whether accidental or intentional), from abuse and from withdrawal.

Adverse events may also occur in screened subjects during any pre-allocation baseline period as a result of a protocol-specified intervention, including washout or discontinuation of usual therapy, diet, placebo treatment or a procedure.

All adverse events will be recorded from the time the consent form is signed through 14 days following cessation of treatment and at each examination on the Adverse Event case report forms/worksheets.

8.2. Definition of an Overdose for This Protocol and Reporting of Overdose to the Sponsor

In this trial, an overdose is any dose higher than 100 mg/day of ertugliflozin or matching placebo or any dose higher than 25 mg/day of ertugliflozin or matching placebo for more than 14 days.

If an adverse event(s) is associated with (“results from”) the overdose of Sponsor's product or vaccine, the adverse event(s) is reported as a serious adverse event, even if no other seriousness criteria are met.

If a dose of Sponsor's product or vaccine meeting the protocol definition of overdose is taken without any associated clinical symptoms or abnormal laboratory results, the overdose is reported as a non-serious Event of Clinical Interest (ECI), using the terminology “accidental or intentional overdose without adverse effect.”

All reports of overdose with and without an adverse event must be reported within 24 hours to Pfizer or designee either by electronic media or paper. Appropriate contact information can be found in the Investigator Trial File Binder (or equivalent).

8.3. Reporting of Pregnancy and Lactation to the Sponsor

Although pregnancy and lactation are not considered adverse events, it is the responsibility of Investigators or their designees to report any pregnancy or lactation in a subject (spontaneously reported to them) that occurs during the trial or within 14 days of completing the trial. All subjects who become pregnant must be followed to the completion/termination of the pregnancy. Pregnancy outcomes of spontaneous abortion, missed abortion, benign hydatidiform mole, blighted ovum, fetal death, intrauterine death, miscarriage and stillbirth must be reported as serious events (Important Medical Events). If the pregnancy continues to term, the outcome (health of infant) must also be reported.

Such events must be reported within 24 hours to Pfizer or designee either by electronic media or paper. Appropriate contact information can be found in the Investigator Trial File Binder (or equivalent).

8.4. Immediate Reporting of Adverse Events to the Sponsor

8.4.1. Serious Adverse Events

A serious adverse event is any adverse event occurring at any dose or during any use of Sponsor's product that:

- Results in death;
- Is life threatening;
- Results in persistent or significant disability/incapacity;
- Results in or prolongs an existing inpatient hospitalization;
- Is a congenital anomaly/birth defect;
- Is a cancer;
- Is associated with an overdose;
- Is an other important medical event.

Refer to [Table 6](#) for additional details regarding each of the above criteria.

Any serious adverse event, or follow up to a serious adverse event, including death due to any cause that occurs to any subject from the time the consent is signed through 14 days following cessation of treatment, whether or not related to the Sponsor's product, must be reported within 24 hours to Pfizer or designee either by electronic media or paper. Appropriate contact information can be found in the Investigator Trial File Binder (or equivalent).

Additionally, any serious adverse event, considered by an Investigator who is a qualified physician to be related to the Sponsor's product that is brought to the attention of the Investigator at any time outside of the time period specified in the previous paragraph also must be reported immediately to Pfizer or designee.

All subjects with serious adverse events must be followed up for outcome.

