- Day 1 has a recommended visit window of ± 5 days relative to S3 (or combined S2/S3 visit); Weeks 6, 12, 18, 26 have a recommended visit window of ± 7 days relative to Day 1.
- All Day 1 procedures to be completed prior to dosing.
- ET = Early termination, subjects who discontinue taking investigational product prematurely should complete procedures for the ET visit and have a 2-week follow-up phone call from their last dose of investigational product. In addition, if subjects agree, they will also be contacted via telephone by the Investigator/qualified designee according to the same schedule as if the subjects were still taking investigational product to assess for SAEs and to collect information on clinical events per [Section 7.6](#) if applicable. See [Section 6.6](#) for additional details.
- Each randomized subject should have a follow-up phone call 14 ± 3 days after the last dose of investigational product to assess for SAEs and to collect information on clinical events per [Section 7.6](#), if applicable.
- Subjects who require glycemic rescue therapy per [Section 5.6](#) must have glycemic rescue therapy initiated at either a scheduled or unscheduled visit, and not by a telephone call.
- Brief physical examination includes assessment of heart, lungs, abdomen and extremities.
- Sitting triplicate blood pressure and pulse rate should be collected, as instructed in [Section 7.4.2](#).
- Duplicate measurements of supine and standing blood pressure and pulse rate should be taken per [Section 7.4.3](#).

- j. ECGs scheduled in the trial are initially assessed at the investigative site for subject safety and then submitted to be read centrally. ECGs should be obtained prior to the nominal time assessment of blood pressure, and pulse rate as well as prior to blood collection.
- k. Samples collected for urinalysis will be sent to the central laboratory for dipstick analysis (not including urinary glucose assessment) and microscopy if the laboratory performed dipstick is positive for blood, nitrites, leukocytes and/or protein.
- l. Urine sample(s) for urinalysis and albumin:creatinine ratio should not be obtained if the subject is menstruating, has vigorously exercised within 24 hours or had fever or an active infection within 2 days of the visit. Under these circumstances, the subject should provide a urine sample for evaluation at an unscheduled visit.

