In the clinical program to date, no clinically significant changes from baseline in serum aminotransferases [ALT (alanine transaminase) and AST (aspartate transaminase)] have been observed.

Phase 3 clinical trial data from another SGLT2 inhibitor, dapagliflozin, revealed a numerical imbalance in the rates of breast and bladder cancer in dapagliflozin-treated subjects compared to control.⁹ The causal relationship to dapagliflozin for this finding is uncertain given the small number of events and the absence of any preclinical signal (ie, no reported increase in either tumor in carcinogenicity studies) with dapagliflozin. Moreover, in the larger clinical program of another SGLT2 inhibitor, canagliflozin, no cancer imbalance, including in breast or bladder cancer events, was reported. Because thorough evaluation of malignancies is important in the development program of all investigational medications, detailed information will be collected for subjects who develop a malignancy. This information could include but is not limited to relevant medical history, biopsy, or operative reports, etc.

Complete information for this compound may be found in the Single Reference Safety Document (SRSD), which for this study is the Investigators' Brochure for ertugliflozin.

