6.6. Subject Withdrawal

Subjects may withdraw from the trial at any time at their own request, or they may be withdrawn at any time at the discretion of the Investigator or sponsor for safety or behavioral reasons, or the inability of the subject to comply with the protocol required schedule of study visits or procedures at a given study site.

If a subject does not return for a scheduled visit, every effort should be made to contact the subject. For withdrawn subjects, the Investigator should inquire about the reason for withdrawal, request the subject return all unused investigational product, request the subject to return for an early termination visit, and follow up with the subject regarding any unresolved adverse events (AEs).

If the subject withdraws from the trial, and also withdraws consent for disclosure of future information, no further evaluations should be performed, and no additional data should be collected. The sponsor may retain and continue to use any data collected before such withdrawal of consent.

Subjects who discontinue treatment with blinded investigational product for reasons other than withdrawn consent should attend the clinic for a visit where all early termination procedures are performed followed by a post-treatment telephone call 14 days after the last dose of blinded investigational product. Thereafter, subjects will be followed by telephone contacts according to the study visit schedule until the end of the trial (Week 26), but will not have other procedures performed that are outlined in the study schedule of activities. The purpose of the telephone contacts, as well as the 14-day post-treatment telephone call, is to collect information about subjects’ health status (ie, evaluate if the subject experienced any SAEs or events eligible for adjudication [see [Section 7.6](#)]).

If a subject indicates his or her intention to stop active participation in the trial (ie, chooses to no longer attend visits at the investigational site, take blinded investigational product, and have other study-related procedures conducted at the investigational site), or if the Investigator has recommended stopping the investigational product, the Investigator must

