8.8. Serious Adverse Events Exempt from Expedited Reporting by the Sponsor

All adverse events meeting SAE criteria (see [Section 8.4.1](#) above) must be reported to the Sponsor within 24 hours of when the site is notified of the event. The following refers to Sponsor processing of SAEs, but does not impact Investigator responsibilities for reporting of any SAE.

Potential pre-specified cardiovascular SAEs will be submitted for adjudication to an independent EAC (see [Section 7.6.1](#) for details).

The following potential cardiovascular SAEs will not be subject to expedited reporting by the Sponsor, even if reported as related to investigational product by the Investigator, unless and until the event is reviewed by the EAC and found not to meet the specified criteria in the EAC charter for that event type:

1. Cardiovascular deaths.

2. Non-fatal myocardial infarction; hospitalization for chest pain or to rule out myocardial infarction, or other hospitalization due to suspected myocardial ischemia where myocardial infarction needs to be ruled out.
3. Non-fatal stroke; TIA, reversible ischemic neurologic deficit (RIND) or other acute ischemic cerebrovascular event where stroke needs to be ruled out.
4. Hospitalization for unstable angina.

As noted above, SAEs that are confirmed by the EAC as one of the pre-specified cardiovascular endpoints (ie, cardiovascular death, non-fatal myocardial infarction, non-fatal stroke, and hospitalization for unstable angina) in the meta-analysis of cardiovascular safety will not be subject to expedited reporting by the Sponsor to Investigators, Ethics Committees/IRBs and regulatory agencies, regardless of causality. Note that all SAEs, including confirmed adjudicated cardiovascular events, will be reviewed and monitored by an E-DMC unblinded to treatment as part of the overall assessment of safety for ertugliflozin. Based upon their regular review of unblinded safety results, the E-DMC is empowered by the E-DMC charter to make recommendations with regard to trial conduct to assure the continuing appropriate safety of the subjects participating in the study.

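### Subjects off study drug are asked about SAEs until Week 26, but reporting regardless of causality ends 14 days after treatment stops, so the sections conflict for unrelated, non-fatal SAEs outside Section 7.6.1

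*Combined protocol and SAP*

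**What the plan says.** **Solicitation.** Section 6.6 keeps subjects who stop investigational product under telephone contact on the visit schedule to Week 26. The purpose of the calls is to "evaluate if the subject experienced any SAEs or events eligible for adjudication". Schedule of Activities footnote d says that subjects who agree are telephoned "according to the same schedule as if the subjects were still taking investigational product to assess for SAEs". Item 11 of Section 6.6.1 is to the same effect, and the text closing that section asks these subjects to return at Week 26.

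**Recording and reporting.** Section 8.1 states: "All adverse events will be recorded from the time the consent form is signed through 14 days following cessation of treatment". The same sentence then adds recording at each examination. Section 8.4.1 requires SAEs to reach the sponsor within 24 hours, related or not, "from the time the consent is signed through 14 days following cessation of treatment". Outside that period it requires a report only of SAEs that the investigator considers related.

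**Other relevant text.** Section 7.6.1 has a separate route for deaths and for the listed cardiovascular, heart-failure and venous thromboembolic events, and it applies after drug is stopped. Section 8.8 opens with a 24-hour duty for events meeting SAE criteria, cites 8.4.1, and gives no end date. It later says that "all SAEs, including confirmed adjudicated cardiovascular events, will be reviewed and monitored by an E-DMC unblinded to treatment". On malignancy, Section 1.4 says that "detailed information will be collected for subjects who develop a malignancy".

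**The concern.** The sections that tell a site what to ask and those that tell it what to record and report run on different clocks. A subject off drug for more than two weeks can be asked about SAEs, can report one, and the site then finds that 8.4.1 asks for nothing further if the event is judged unrelated.

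The causality condition matters because late off-drug events are likely to be called unrelated. Table 6 directs a negative answer where the timing is not reasonable or another cause is obvious, and Section 6.6 lets these subjects start other therapies. Cancer is a relevant case: Section 1.4 singles it out and 8.4.1 lists it as serious. If sites resolve the conflict differently, ascertainment of late SAEs will vary by site and by individual causality opinion. Section 9.3 gives no rule for SAEs that start well after the last dose.

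**Working it through.** The plan gives no figure on this point to reproduce. The check has two parts: a comparison of the text, and a sizing of the time affected.

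**1. The rules side by side, for a subject off drug**

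| Section | Duty | Ends | Causality condition |
|---|---|---|---|
| 6.6, 6.6.1 item 11, footnote d | Ask about SAEs and adjudicable events | Week 26 | None |
| 8.1 | Record AEs | 14 days after treatment stops, plus each examination | None |
| 8.4.1, main rule | Report SAEs in 24 hours | 14 days after treatment stops | None |
| 8.4.1, later events | Report SAEs immediately | No end | Must be judged related |
| 7.6.1 | Send and adjudicate deaths and listed cardiovascular, heart-failure and thromboembolic events | End of study | None |
| 7.6.2 to 7.6.5 | Adjudicate fracture, pancreatitis, liver and renal events | No off-drug period stated | None stated |
| 8.8 | Report SAEs in 24 hours of site notification | Not stated | None |

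**2. One case followed through**

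A subject stops drug at Week 4, so the 14-day window closes at Week 6. Contacts remain at Weeks 12, 18 and 26. At Week 18 the subject reports a recent non-fatal serious infection, judged unrelated.

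- Section 6.6: the site was meant to ask.
- Section 8.1: past 14 days, and a telephone call is not clearly an examination.
- Section 8.4.1: outside the main rule, and outside the rule for later events because it was judged unrelated.
- Section 7.6.1: not a listed event.
- Section 8.8: reportable if read literally.

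The answer depends on which section the site applies. Removing related SAEs, deaths and the 7.6.1 events leaves non-fatal, unrelated SAEs outside 7.6.1, with onset more than 14 days after the last dose.

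**3. Time affected**

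Inputs: 26 weeks of treatment and a 14-day window; about 495 randomised and 20% drop-out (Section 9.1). Assumptions: stopping times are uniform over 26 weeks; 5%, 10% or 20% stop drug and accept calls.

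- Weeks solicited beyond the window, for a stop at week w: max(0, 26 − (w + 2)). This gives 18 at Week 6, 12 at Week 12, 6 at Week 18 and 0 from Week 24.
- Mean per subject who stops: (24² / 2) / 26 = 288 / 26 = 11.08 weeks.
- Planned follow-up: 495 × 26 = 12,870 subject-weeks.

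| Stop drug | Subjects | Subject-weeks (× 11.08) | Subject-years (÷ 52.18) | Share of 12,870 |
|---|---|---|---|---|
| 5% | 24.75 | 274 | 5.3 | 2.1% |
| 10% | 49.5 | 548 | 10.5 | 4.3% |
| 20% | 99 | 1,097 | 21.0 | 8.5% |

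The documents give no SAE rate. If one assumes 5 to 10 SAEs per 100 subject-years, the expected count over all three arms is 5.3 × 0.05 ≈ 0.3 to 21.0 × 0.10 ≈ 2, before removing related SAEs, deaths and 7.6.1 events.

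**The case against.** The best reply is that the protocol covers most of this ground elsewhere.

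- **Section 7.6.1** takes deaths and the main cardiovascular and thromboembolic events to study end without regard to causality. This stands, and it removes the gravest events from the gap. It does not reach cancer, serious infection or most other hospitalisations.
- **Section 8.8**, read literally, makes every SAE reportable within 24 hours of notification, and its reference to 8.4.1 can be taken as pointing only to the SAE definition. That reading is fair. It also means 8.8 contradicts the causality limit in 8.4.1, so it shows a conflict rather than resolving one.
- **Section 8.1** adds recording at each examination, and subjects off drug are asked back at Week 26. That visit may well be covered. A telephone call is not clearly covered, and nothing in 8.1 extends 8.4.1.
- **Section 1.4** sets no time limit on collecting malignancy details, so the plan cannot be said to intend that late cancers be lost. It gives the site no reporting instruction, however.
- **The exposure is small.** This stands. The 20% also counts rescued subjects, who stay on drug, and study withdrawals; and footnote d makes the calls conditional on agreement.

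A reader might infer that all late SAEs go unreported, that SAE counts by arm will be biased, or that the E-DMC statement in 8.8 will be breached. The documents do not support these. Several routes remain open, no differential stopping by arm is shown, and what the E-DMC sees and how SAEs are tabulated depend on its charter and on detail that Section 9 leaves to the SAP.

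**Conclusion.** The point holds as an inconsistency between sections, limited to non-fatal SAEs judged unrelated, outside Section 7.6.1, and starting more than 14 days after the last dose in subjects who stop drug early and stay in contact. For fracture, pancreatitis, liver and renal events, Sections 7.6.2 to 7.6.5 provide adjudication but no off-drug reporting period.

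The time affected is about 2% to 9% of planned follow-up. That rests on even stopping times, on 5% to 20% stopping, and on those subjects accepting calls; the top of the range is a ceiling. It measures time at risk of the conflict, not missed SAEs, which on any plausible rate would be few. The matter should be corrected because it concerns complete SAE ascertainment and costs little. It does not threaten the efficacy conclusions.

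**What to change.** Reconcile Sections 6.6, 8.1, 8.4.1 and 8.8 by stating the period once and referring to it from each. For subjects who stop investigational product early and remain in contact, all SAEs and events eligible for adjudication are recorded and reported within 24 hours, regardless of causality, through the later of Week 26 or 14 days after the last dose. This would also supply the period missing from 7.6.2 to 7.6.5. Non-serious AEs can keep the 14-day limit.

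SAEs with onset more than 14 days after the last dose can be flagged separately in the safety tables, so that on-treatment summaries stay interpretable.

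The cost is one sentence per section and a few more SAE forms. The calls are already planned.
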